## **4. Introduction**

### **4.1. Background of development**

Peripheral arterial disease (PAD) is a common disease characterized by atherosclerotic stenosis and occlusion in peripheral arteries. Its prevalence is in the range of 3 – 10% with increasing with age (about 15 – 20% in people of age over 70-year old). It most affects lower extremities vessels causing claudication, about 5% of the patients eventually develop critical limb ischemia (CLI) with a poor prognosis – amputation in 30% and death in 25% of those with CLI at 1 year.

Previous studies show that the prevalence of lower extremity artery disease (LEAD) in China is 2.1 – 27.5% in general population. But as one of the most rapidly aging nations (the age of > 65-year old was 9% of its population in 2011, expecting double by 2020), the prevalence will increase remarkably in the near future.

The femoropopliteal artery is the most commonly involved site in patients with PAD. Endovascular therapy, percutaneous transluminal angioplasty (PTA) with optional bailout stenting is currently recommended for the majority of symptomatic patients by ACCF/AHA and TASC II. For calcified lesions, treatment with PTA may not provide sufficient revascularization and stenting is often required. However, inadequate stent expansion is more likely to occur in such calcified lesions and there is a concern that the risk of in-stent restenosis and thrombotic events may be increased. In order to improve the clinical outcomes, novel technologies of debulking of the extensive atheromatous burden has emerged with promising clinical outcomes of atherectomy of femoro-popliteal lesions.

JETSTREAM™Atherectomy System (Jetstream) is one of these atherectomy systems, and was approved under 510(K) for the Pathway PV System, a first- generation model, in July 2008, and later in April 2013, for the current model. Jetstream Atherectomy System was also granted a CE mark in September 2013 and is currently marketed in the United States, Europe, Austria, and other regions.

### **4.2. Clinical Study Summary**

#### **4.2.1. Pathway PVD clinical study**

The Pathway PVD clinical study was a prospective, multicenter, single arm study conducted using the Pathway PV System, a first-generation model of Jetstream, in which a total of 172 subjects were enrolled at 9 investigational sites in Germany, Austria, and Belgium.

The primary safety endpoint was the freedom from major adverse events (MAE) including clinically driven target lesion revascularization (TLR), any death, target vessel revascularization (TVR), myocardial infarction (MI), and index limb amputation at 30 days post procedure. The primary effectiveness endpoint was a reduction in mean percent stenosis, with and without adjunctive therapy.

The secondary endpoints included: (1) MAE at 6 months, (2) absence of death or amputation as a result of the Pathway PV System during the follow-up period, (3) clinical success defined as  $\geq 1$  clinical category improvement of Rutherford scale (or equivalent) from baseline at 6 and 12 months; (4) hemodynamic success defined as a  $> 0.1$  improvement in the ABI during the period from baseline to 30 days post procedure and no deterioration  $> 0.15$  from the maximum early post procedure level at 6 and 12 months. Target lesions had reference vessel diameters ranging from 3 – 5 mm (visual estimation), total lesion lengths (alone or series of lesions) up to 10 cm for the femoropopliteal arteries as well as up to 3 cm for the tibial or peroneal arteries (Rutherford categories 1–5 or equivalent).

The 30-day freedom from MAE was 99% (170/172), with 2 amputations planned prior to the intervention being performed (Table 4.2-1). No procedure or device related amputations occurred.

**Table 4.2-1: Major Adverse Events at 30 Days and 6 Months**

	30 Days (n=172)	6 Months (n=162)
MAE	2 (1.1%)	31 (19%)
TVR	0 (0%)	4 (2.5%)
Death*		
Sudden Cardiac Arrest (probable)	0 (0%)	1 (0.6%)
Amputation	2 (1.1%)	2 (1.2%)
TLR	0 (0%)	25 (15%)
Non-Q wave MI	0 (0%)	1 (0.6%)

At the 6-month follow-up, 31 subjects had at least 1 MAE. The freedom from serious adverse device effects (SADEs) and TLR at 6 months post-procedure, was 85% with a 95% lower confidence interval of 78%.

Success in crossing and debulking the target lesion was achieved in 99% (208/210) of the cases. Thirty-three percent of the cases were atherectomy procedures alone, while in 59% of the lesions, adjunctive low-pressure angioplasty was also employed. Stenting was indicated in 7% of the subjects. Mean diameter stenosis was reduced from  $79.4\% \pm 17.7\%$  at baseline to  $35.0\% \pm 16.1\%$  after atherectomy. After adjunctive therapy, the diameter stenosis was further reduced to  $21.4\% \pm 10.5\%$ . Interventional success, defined as residual stenosis  $\leq 30\%$  by visual estimation, was achieved in 209/210 (99%) lesions.

Clinical success was achieved in 68% (91/133) at 6 months and 70% (75/107) at 12 months, based on improvement in Rutherford classification. Hemodynamic success was achieved in 52% (63/121) subjects at 6 months and in 52% (51/98) at 12 months.

Primary and secondary duplex-documented patency rates at 12 months were 61.8% (76/123 lesions) and 81.3% (100/123 lesions), respectively. Clinically driven TLR rates were 15% (25/172) at 6 months and 26% (42/162) at 12 months, while TVR rates (including TLR) were 17% (29/172) and 30% (49/162), at 6 and 12 months respectively.

Additional evaluation of the Pathway PVD Trial dataset was completed by Sixt et al, the focus of which was to evaluate the changes in Quality of Life (QOL) following atherectomy. The primary endpoint was evaluation of the QOL using the 5-point Walking Impairment Questionnaire (WIQ) scale. The primary safety endpoint was freedom from MAE, including clinically driven TLR, any death, TVR, MI, and index limb amputation at 30 days post-procedure, previously reported by Zeller et al. Secondary endpoints were also previously reported. The subject cohort improved from baseline by an average of 0.94 points in the WIQ at 30-days post procedure, 0.78 points at the 6 month follow-up and 1.07 points at the 12 month follow-up. When comparing subjects with and without restenosis, a significant improvement in the WIQ was observed at 6 months, but not at the 12-month follow-up. Twenty-five (25) procedure-related serious adverse events were reported in the 158 subjects at the 6 month follow-up. These events included 18 (11%) TLR, 1 (0.6%) TVR, 3 (1.9%) emboli, 1 (0.6%) dissection, 1 (0.6%) abrupt closure, and 1 (0.6%) re-intervention in the target limb. All were treated without permanent injury, amputation, or death. An additional serious adverse event was noted at 4 days post-procedure where one participant experienced a cerebral infarct and was treated with drug therapy. The overall conclusion is that the Jetstream Atherectomy device for infrainguinal treatment of atherosclerotic lesions significantly improved the quality of life, as evaluated by the 5 point WIQ. Additionally, the clinical data and analyses support the Jetstream device as safe and effective.

Additional analysis of data from the Pathway PVD Trial was completed by Sixt et al, the goal of which was to determine whether the Jetstream Atherectomy system produced different outcomes in subjects with and without type 2 diabetes mellitus (DM). For the 172 subjects enrolled in the Pathway PVD Trial, 80 subjects were in the DM group and 92 were in the non-DM group. Lesion characteristics did not differ between the two groups, although the DM group had significantly higher body weight ( $p<0.001$ ) and body mass index ( $p<0.001$ ). Procedure related adverse events were documented in 49% (39/80) of the DM group and 43% (40/92) of the non-DM group. At the 30 day follow-up, the MAE rate for the DM group was 2.5% (2/80) and 0% (0/92) in the non-DM group. At the 6 and 12 month follow-ups, MAE rates were 13.8% (11/80) and 25% (20/80) in the DM group compared to 21.7% (20/92) and 31.5% (29/92) in the non-DM group, respectively. The 12 month TLR rate was 20% (16/80) in the DM group and 28% (26/92) in the non-DM group. During the study period 1 (1.3%) DM subject died, due to probable sudden cardiac arrest, at approximately 50 days post-procedure and 1 (1.1%) non-DM subject died due to non-Q wave MI, at 5 months post-procedure. The latter death was noted previously as occurring after the 6-month dataset was analyzed. Other assessments (ABI, Rutherford Class, Walking Impairment) did not differ between the DM and non-DM groups. The overall conclusion was that the Jetstream Atherectomy system in complex infrainguinal arteries provides comparable and acceptable outcomes in DM and non-DM patients.

In summary, conclusions from the Pathway PVD Trial support that the Jetstream Atherectomy System is safe and effective for treating obstructive lesions with a maximum lesion length of 10 cm in infrainguinal arteries with a reference vessel diameter of 3 mm to 5 mm.

#### 4.2.2. Jetstream Calcium Study

The Jetstream Calcium Study was a prospective, single-arm, multicenter study to evaluate the Jetstream Atherectomy System for severely calcified femoral-popliteal artery lesions, i.e., subjects with claudication and lesions with superficial calcium  $> 90^\circ$  and  $> 5$  mm in length as determined by intravascular ultrasound (IVUS). The 2.1 mm catheter was used in this study without distal protection. This study enrolled 26 subjects with eligible lesions in the SFA, popliteal artery, and tibial artery.

The primary effectiveness endpoint was calcium removal and luminal gain measured by comparing pre-intervention to post-atherectomy intravascular ultrasound (IVUS) images. Secondary endpoints included (1) Major adverse events (MAE), defined as death, myocardial infarction, amputation, and target lesion or vessel revascularization up to 30 days; (2) adjunctive therapy use; and (3) residual diameter stenosis.

The visually assessed angiographic diameter stenosis improved from  $89 \pm 9\%$  pre-treatment to  $37 \pm 13\%$  post atherectomy and finally to  $10 \pm 6\%$  post adjunctive treatment. After matching pre- and post atherectomy IVUS segments, the treated segment median length measured 36 mm. The segment of superficial calcium with calcium reduction measured 13mm in median length, or 37% of the entire treated segment. The IVUS findings from pre to post atherectomy at the lesion level showed that the minimum lumen area increased from  $5.1 \pm 2.8 \text{ mm}^2$  to  $8.3 \pm 2.6 \text{ mm}^2$  ( $p < 0.0001$ ) and area stenosis decreased from  $64 \pm 17\%$  to  $41 \pm 18\%$  ( $p < 0.0001$ ). By comparing pre- and post- atherectomy IVUS images, the slice with maximum calcium reduction was identified; the lumen area in these slices increased from  $6.6 \pm 3.7 \text{ mm}^2$  to  $10.0 \pm 3.6 \text{ mm}^2$  ( $p = 0.0001$ ). The decrease in calcium area, measured as  $2.8 \pm 1.6 \text{ mm}^2$ , was responsible for  $86 \pm 23\%$  of the lumen area increase (Table 4.2-2).

**Table 4.2-2: Intravascular Ultrasound Findings – 26 Lesions**

		Pre-treatment	Post-atherectomy	p-value
Proximal reference lumen area (mm^2)		$14.6 \pm 5.1$	$14.5 \pm 5.2$	0.91
Distal reference lumen area (mm^2)		$14.8 \pm 6.2$	$14.7 \pm 5.9$	0.97
Minimum lumen area site	Lumen area(mm  )	$5.1 \pm 2.8$	$8.3 \pm 2.6$	<0.0001
	Minimum lumen diameter(mm)	$2.0 \pm 0.4$	$2.8 \pm 0.4$	<0.0001
	Lumen symmetry index	$0.70 \pm 0.13$	$0.76 \pm 0.14$	0.11
	Area stenosis (%)	$64 \pm 17$	$41 \pm 18$	<0.0001
Maximum calcium ablation site	Lumen area(mm  )	$6.6 \pm 3.7$	$10.0 \pm 3.6$	0.001
	Minimum lumen diameter(mm)	$2.3 \pm 0.5$	$3.0 \pm 0.5$	<0.0001
	Lumen symmetry index	$0.70 \pm 0.14$	$0.70 \pm 0.14$	0.26
	Area stenosis (%)	$53 \pm 23$	$29 \pm 22$	0.0005
	Maximum superficial calcium (°)	$151 \pm 70$	$146 \pm 71$	0.83
	Decrease of calcium area(mm  )	NA	$2.8 \pm 1.6$	NA
	Calcium reduction (%)	NA	$86 \pm 22$	NA

Surface Shape of calcium	Convex	58% (15)	27% (7)	0.02
	Concave	42% (11)	73% (19)	
Irregularity of superficial calcium	Irregular	54% (14)	39% (10)	0.27
	Smooth	46% (12)	61% (16)	
	Reverberation	31% (8)	39% (10)	0.58
	Maximum arc of Reverberation (°)	23±20	65±40	0.006
Values are mean ± standard deviation or (n).				

The Jetstream system removed and modified moderate to severe superficial calcium to achieve significant lumen gain, and as shown in Table 4.2-3 adjunctive balloon angioplasty after calcium modification showed further lumen increase without major complications. No major adverse events occurred up to 30 days post procedure.

**Table 4.2-3: Intravascular Ultrasound Findings - 11 Lesions with Adjunctive Balloon**

		(1) Pre-treatment	(2) Post-atherectomy	(3) Post-balloon	p-value	
					1 vs .2	2 vs .3
Proximal reference lumen area (mm  )		15.1	14.6	17.7	0.15	0.013
Distal reference lumen area (mm  )		16.1	16.4	18.5	0.55	0.083
Minimum lumen area site	Lumen area(mm  )	4.4	7.1	11.9	<0.001	<0.001
	Minimum lumen diameter(mm)	2.0	2.7	3.4	<0.001	<0.001
	Lumen symmetry index	0.74	0.81	0.76	0.13	0.33
	Area stenosis (%)	70.9	51.8	34.2	<0.001	<0.001
Maximum calcium ablation site	Lumen area(mm  )	6.3	9.3	13.3	<0.001	<0.001
	Minimum lumen diameter(mm)	2.3	3.0	3.6	<0.001	<0.001
	Lumen symmetry index	0.74	0.79	0.76	0.029	0.37
	Area stenosis (%)	59.2	38.1	27.8	<0.001	0.042
	Maximum superficial calcium (°)	164	164	162	0.99	0.88
	Decrease of calcium area(mm  )	NA	2.4	NA	NA	NA
	Calcium reduction (%)	NA	94	NA	NA	NA

Surface Shape of calcium	Convex	55%	9%	9%	0.018	0.99
	Concave	46%	91%	91%		
Irregularity of superficial calcium	Irregular	55%	27%	9%	0.25	0.33
	Smooth	45%	73%	9%		
Reverberation		27%	73%	36%	0.99	0.99
Maximum arc of Reverberation		26°	102°	36°	<0.001	<0.001
Dissection		0%	27%	73%	0.01	

The study found that the Jetstream Atherectomy System removed and modified superficial calcium to achieve significant lumen gain. Adjunctive balloon angioplasty after calcium modification showed further lumen increase without major complications.

## 5. Device Description

The test device is intended to be used as adjunctive therapy for percutaneous intervention to remove atherosclerotic disease, debris, and thrombus from the SFA and/or PPA.

The JETSTREAM™ Atherectomy System is a rotational atherectomy catheter system designed for use in debulking and treating vascular disease in the peripheral vasculature. The catheter includes multiple distal ports located at the catheter tip, which are designed to provide independent infusion and aspiration functions for the active removal of fluid, excised tissue and thrombus from the peripheral treatment site. The Jetstream System consists of two primary components that are packaged separately; Atherectomy Catheter (Jetstream Catheter) set and Atherectomy Console (Jetstream Console) (Figure 5.1-1).

Jetstream Catheter Set

Jetstream Console

Figure 5.1- 1: JETSTREAM™Atherectomy System

## 5.1. Jetstream Catheter

Jetstream Catheter set is a sterile, single use unit consisting of an electrically driven Catheter and Control Pod with detachable Activation Handle. The Catheter utilizes a differentially cutting tip and includes both aspiration and infusion capabilities. The Activation Handle provides a user interface with keypad controls for device operation. The unit, its electrical connectors, tubing, and aspirant collection bag are packaged in a single pouched tray with retention lid, and sterilized with ethylene oxide (EO). Note that the tray retention lid is not a sterile barrier.

The catheter has four types of model based on existence of expandable blade and size of catheter tip as shown in Table 5.1-1 and Figure 5.1-2. The Jetstream single cutter (SC) catheters are available in 1.6mm and 1.85mm sizes and the Jetstream expandable cutter (XC) catheters are available in 2.1mm (Blade Down)/3.0mm (Blade Up) and 2.4mm (Blade Down)/3.4mm (Blade Up). XC model has a mechanism that expandable blade is fold when blade down and expandable blade rises up (i.e. Blade Up) when MAX button in the control pod is turned on.

**Table 5.1-1: Jetstream Catheter Specifications**

Model	Catheter Length (cm)	Tip Diameter (mm)	Minimum Matched Introducer Size (F)	Maximal Matched Guidewire Diameter (inch)	Maximum Catheter Profile (mm)
Jetstream XC 2.1/3.0	135	2.1/3.0	7	0.014	2.5
Jetstream XC 2.4/3.4	120	2.4/3.4	7	0.014	2.45
Jetstream SC 1.6	145	1.6	7	0.014	2.33
Jetstream SC 1.85	145	1.85	7	0.014	2.33

[figure not shown]

Figure 5.1- 2: Jetstream Catheter Tip

## **5.2. Jetstream Console**

A reusable PV Console consists of two (2) peristaltic pumps for aspiration and infusion, power supply, system controller, keypad interface, and LED indicators for device operational status. The PV Console mounts on a standard IV stand and remains outside the sterile field during the procedure (Figure 5.1-1).

## **5.3. Intended Use**

The Jetstream System is intended for use in atherectomy of the peripheral vasculature and to break apart and remove atherosclerotic disease, debris, and thrombus from the SFA and/or PPA.

## **5.4. Device Labeling**

The copies of the Directions for Use (DFU) for the Jetstream System are included in the JETSTREAM CHINA Manual of Operations, including the DFU for the Jetstream console and DFUs for the Jetstream catheters and control pod. The labeling will include at least the following information:

- Product Name
- Universal Part Number (UPN)
- Lot number
- Project Name, Storage & Shipment condition
- Expiration (use by) date

The following statements appear on the JETSTREAM CHINA product labeling for clinical distribution:

### **Caution: For Clinical Trial Use Only**

Device labeling will be provided in Chinese per China regulations.

## **6. Study Objectives and Endpoints**

### **6.1. *Study Objectives***

The primary objective of this study is to evaluate the safety and effectiveness of JETSTREAM™ Atherectomy System (Jetstream) for treating symptomatic Chinese patients with occlusive atherosclerotic lesions in native superficial femoral artery (SFA) and/ or proximal popliteal arteries (PPA) during percutaneous peripheral vascular intervention.

## 6.2. *Study Endpoints*

### 6.2.1. Primary Endpoints

#### 6.2.1.1. The primary safety endpoint:

The primary safety endpoint is the rate of major adverse event (MAE), defined as all-cause death, target limb unplanned major amputation and/or target lesion revascularization (TLR), within 30 days post index procedure.

#### 6.2.1.2. The primary effectiveness endpoint:

The primary effectiveness endpoint is the acute reduction of percent diameter stenosis (%DS) post atherectomy but prior to any adjunctive therapy, when compared to its baseline diameter stenosis (absolute mean percentage).

### 6.2.2. Additional Endpoints

- Procedural success, defined as  $\leq 30\%$  residual angiographic stenosis in 2 near-orthogonal projections by visual assessment, after successfully debulking the target lesion and adjunctive interventions (such as percutaneous transluminal angioplasty/stenting) without any MAE within 24 hours post index procedure
- Primary vessel patency of the treated segment assessed by duplex ultrasound sonography (DUS) at 6 and 12 months post-procedure without TLR\*
- Clinical success rate (defined as improved Rutherford classification by at least +1 class compared to baseline) at 30 days, 6 and 12 months
- Hemodynamic success rate (defined as positive change in Ankle-Brachial Index) at 30 days, 6 and 12 months
- MAE rate 6 and 12 months post-index procedure
- All-cause death at 30 days, 6 and 12 months
- Clinically-driven TLR and TVR rate at 30 days, 6 and 12 months
- Target limb major amputation at 30 days, 6 and 12 months
- Rate of peri-procedural complications:
  - Perforation at treated segment
  - Abrupt closure at treated segment (including dissection and thrombosis)
  - Significant dissection (types C – F) at treated segment
  - Aneurysm at treated segment
  - Distal embolization

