	
**The before-and-after atherectomy in the Pathway PVD shows 79.4%±17.7% and 35.0%±16.1% respectively. The before-and-after atherectomy in Jetstream Calcium study shows 86.9%±9.0% and 37.0%±13.0%. The before-and-after atherectomy in JET Registry shows 91.1%±9.8% and 44.4%±20%, and the acute reduction of %DS is 46.7%±20.5%.

Success Criteria for the PG Study	
Success Criteria for Primary Safety Endpoint Jetstream System will be concluded as meeting PG for device safety if the one-sided lower 97.5% confidence bound on the observed 30-day MAE-free rate is greater than 88%.
 
Success Criteria for Primary Effectiveness Endpoint Jetstream System will be concluded as meeting endpoint for device effectiveness if the one-sided lower 97.5% confidence bound on the difference between before and after atherectomy in %DS within subject is greater than zero.
 
Success Criteria for the Study If the primary safety and the primary effectiveness endpoints are both met, the study will be considered a success and both device safety and effectiveness will be claimed.

Sample Size Parameters	
The overall sample size is consist of the primary cohort and roll-in subjects. The sample size of primary cohort is driven by the primary safety endpoint.
 
 
• Power ≥ 90%
 
• One-sided overall significance level = 2.5% (alpha)
 
• PG for 30-day MAE-free rate = 88%
 
• Expected 30-day MAE-free rate = 99%
 
• Attrition rate = 15% (loss to follow-up at 30 days)
 
• A minimum of 50 subjects to be evaluable at 30 days that will provide at least 99% power for the primary safety endpoint
 
• A sample size of 60 subjects to be enrolled in the primary cohort at baseline
 
 
With additional 2 roll-in subjects per site, the overall subjects to be enrolled are approximately 80.

Prospective, non-randomized, multicenter clinical study of the JETSTREAM™ Atherectomy System (Jetstream) in treatment of occlusive atherosclerotic lesions in the superficial femoral and/ or proximal popliteal arteries in Chinese patients (JETSTREAM CHINA)	
Core Lab	All angiographic and DUS readings will be assessed by independent core laboratories

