### **Procedural recommendations:**

- Optimal target lesion/vessel treatment is recommended.
- Bailout stenting with a commercially-available stent or by-pass surgery may be performed at the discretion of operating physician, if the attempts with PTA have resulted any of the following:
  - Final residual stenosis at the target lesion being > 30% by visual assessment
  - Occurrence of Grade C or greater dissection (NHLBI)
  - Occurrence of clinically apparent perforation requiring treatments
  - Occurrence of any obstructive complication (e.g., recoil) demonstrating a marked decrease in the flow in the target vessel
- Angiographic complications, such as distal embolism or no reflow, should also be treated per standard practice. All angiographic complications during procedure should be documented by angiography and submitted to the Angiographic Core Laboratory for analysis.

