#### **10.6.3. Post-procedure Angiogram**

Perform the post-procedure angiography according to the Angiographic Core Laboratory procedure guidelines. The final angiogram must be performed and recorded, including distal run-off. Angiographic images must be sent to the angiographic core laboratory for evaluation.

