#### **11.3.2. Control of Systematic Error/Bias**

Selection of subjects will be made from the investigators' general or professional referral population. All subjects meeting the inclusion/exclusion criteria that have signed the protocol-specific ICF will be eligible for enrollment in the trial. Consecutively eligible subjects should be enrolled into the study to minimize selection bias. In determining subject eligibility for the study, the investigator's assessment of imaging will be used. The effectiveness endpoint data obtained from the core laboratory and the safety adjudicated data from independent Clinical Event Committee (CEC) will be used for the primary analyses.

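### Procedural and technical success are scored on a visual stenosis reading by an unnamed reader, while the core-laboratory reading of the final angiogram is committed only to the primary analyses

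*Protocol*

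**What the plan says.** Protocol 6.2.2 and both synopses define procedural success by a cut-off of 30% or less on "residual angiographic stenosis in 2 near-orthogonal projections by visual assessment, after successfully debulking the target lesion and adjunctive interventions", together with freedom from major adverse events in the first 24 hours. Protocol Table 25.2-1 defines technical success with the same visual cut-off and builds procedural success on it. SAP 5.1 repeats the protocol definition. SAP 5.12 gives a separate technical-success definition that is also visual at 30%.

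Protocol 10.6.1, under its procedural recommendations, lists the findings after balloon angioplasty that permit bailout stenting or bypass. The first is "Final residual stenosis at the target lesion being > 30% by visual assessment". Bailout "may be performed at the discretion of operating physician", so it is allowed and not required.

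On imaging, Protocol 10.6.3 states "The final angiogram must be performed and recorded, including distal run-off" and then "Angiographic images must be sent to the angiographic core laboratory for evaluation". The Core Lab row of the synopsis states "All angiographic and DUS readings will be assessed by independent core laboratories". SAP 5.7 has the core laboratory read index-procedure angiograms both qualitatively and quantitatively. Protocol 12.3, however, names only baseline angiograms and the 6- and 12-month ultrasound recordings as records that centres send.

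Protocol 11.3.2 and SAP 4.2 say which data the primary analyses use: "The effectiveness endpoint data obtained from the core laboratory" and the adjudicated safety events. Neither document assigns the core-laboratory reading of the final angiogram to procedural or technical success, even as a supportive result.

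**The concern.** Core-laboratory data appear in Protocol 11.3.2 as a bias control, but that control stops at the primary endpoints. Procedural success is the first additional endpoint listed, and SAP 5.1 puts it in both the 30-day and the 12-month reports. Protocol 18.4 names better procedural success as an anticipated benefit.

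If the operator makes the visual reading, the person who treated the lesion also scores the result, on the same cut-off that bears on whether to treat further. There is no control arm in which the same leniency would appear and cancel out. A reader of the report could not tell how much of a high rate reflects the vessel and how much reflects the reader, although an independent reader receives the same images.

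**Working it through.** The documents give no expected rate, power or sample size for procedural success, so there is no planned figure to reproduce. The check is a comparison of passages, then two calculations that show what can and cannot be said about size.

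**Passages side by side**
- Scoring rule: success if visual residual stenosis is 30% or less after adjunctive treatment (Protocol 6.2.2, Table 25.2-1; SAP 5.1, 5.12).
- Treatment rule: bailout permitted if visual residual stenosis is above 30% after balloon angioplasty (Protocol 10.6.1). This is the exact complement of the scoring rule.
- Independent reading: images required and sent (Protocol 10.6.3), read quantitatively (SAP 5.7), used for the primary analyses (Protocol 11.3.2; SAP 4.2), and not assigned to this endpoint.
- Protocol 12.3 taken literally would exclude the final angiogram. It would also exclude the post-atherectomy image that the primary effectiveness endpoint needs, so its list looks too narrow.

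**Check 1: the Pathway PVD figures (Protocol 4.2.1)**
- Visual success: 209/210 = 99.5% of lesions (printed as 99%).
- Residual stenosis after adjunctive therapy: mean 21.4%, SD 10.5%. Under a normal distribution, P(X ≤ 30) = Φ((30 − 21.4)/10.5) = Φ(0.819) = 79.4%.
- The gap between 99.5% and 79.4% could come from readings or treatment steered to the threshold, but it does not prove that. If all values lay between 0 and 30 with mean 21.4, the SD could be as large as √((30 − 21.4) × 21.4) = √184.04 = 13.6. An SD of 10.5 is therefore arithmetically compatible with every lesion at or below 30%. The documents also do not say that the mean and the success rate come from the same reader.

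**Check 2: illustration with assumed inputs**
Residual stenosis after balloon angioplasty is set at 21.4 ± 10.5 (the Pathway PVD post-adjunctive figures) and after bailout at 10 ± 6 (the Jetstream Calcium Study post-adjunctive figures, Protocol 4.2.2). Operator reading error has SD 5 or 10 points, operator bias is 0, −5 or −10 points, and core-laboratory error has SD 5. None of these is a planning value of the trial. The gap is operator minus core laboratory, taken within each setting.

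| Trigger acted on | Operator-scored success | Core-laboratory-scored success | Gap (points) |
|---|---|---|---|
| Never | 72.4% to 94.5% | about 77% | −4.6 to 17.5 |
| Half the time | 85.6% to 97.2% | 79.6% to 84.7% | 1.5 to 17.6 |
| Always | 98.8% to 100% | 82.0% to 92.4% | 7.5 to 18.0 |

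Three things follow under these assumptions:
- The operator-scored rate is nearly fixed only when the trigger is always, or almost always, acted on.
- With zero systematic bias and the trigger always acted on, the gap is still about 7.5 points, because one reading error decides both whether to stop and how the result is scored.
- The core-laboratory rate also rises as bailout is used more, because bailout lowers the stenosis in the model. An independent reading does not remove that effect.

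**The case against.** A reader might infer that the same person makes both readings and that the rate is close to self-fulfilling. Applying the Pathway PVD rate to the primary cohort gives 60 × 209/210 = 59.7, hence 59 or 60 successes whatever the true stenosis. The documents do not support this:
- The success definitions name no reader. Protocol 10.6.1 does name the operating physician when describing the guidewire check, and the synopsis gives all angiographic readings to core laboratories. That the operator is the reader is a natural inference, not a stated fact.
- Bailout is discretionary.
- The figure reported as "by visual estimation, was achieved in 209/210 (99%) lesions" counts lesions on stenosis alone. Here the unit is the subject, and success also needs debulking and 24 hours without a major adverse event.
- No bailout rule is documented for Pathway PVD, and stenting was indicated in 7% of its subjects. Its lesions ran to 10 cm in femoropopliteal vessels of 3 to 5 mm; this trial takes up to 15 cm in 3 to 6 mm.

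It can also be said that treating to a threshold is not assessor bias, since the endpoint is meant to describe the result after adjunctive treatment. In addition, Protocol 11.3.4 and SAP 4.4 already plan summaries of site-reported and core-laboratory lesion characteristics and procedure assessments. The first argument stands and limits what the fix can achieve. The second helps only in part: neither section mentions residual stenosis or links the core-laboratory value to success.

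Finally, the endpoint is observational (Protocol 11.3.5; SAP 5.1) and plays no part in study success (Protocol 11.2; SAP 3.3). That stands and sets the weight of the point.

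**Conclusion.** The point holds as a minor one. A visual reading by an unnamed reader scores the endpoint at the cut-off that also permits bailout, and the independent reading is not assigned to it. The residual-stenosis component is therefore open to assessor bias. The debulking and 24-hour event components do not depend on the 30% reading.

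The direction would favour success if the reader is the operator and reads leniently; both are assumptions. The size cannot be derived from the documents, and the gaps in the illustration depend wholly on its assumed errors, biases and bailout uptake. The primary angiographic endpoint, which already uses core-laboratory data, and the study conclusion are unaffected.

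**What to change.** In both synopses, Protocol 6.2.2, Protocol Table 25.2-1 (technical success, and through it procedural success), SAP 5.1 and SAP 5.12:
- Name the reader, and score residual stenosis of 30% or less from the core-laboratory reading of the final angiogram.
- Report the visual result beside it as supportive, naming who read it. This keeps a version comparable with Pathway PVD.
- Report the bailout rate in the same table, so that treatment to the threshold is visible.
- State how subjects with no readable final angiogram are counted.

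SAP 5.12 needs rewording in any case, because it describes delivery of a study stent, which is not the test device. Reconcile Protocol 12.3 with Protocol 10.6.3 and SAP 5.7 so that the final angiogram is plainly among the records sent. Leave operator decisions during the procedure as they are.

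The cost is definition wording in the protocol and an amended SAP before the primary endpoint analysis, as Protocol 11.3.10 and SAP 5.16 provide. No new imaging or visit is needed. Confirm from the core-laboratory guidelines, which are not among these documents, that final residual stenosis is measured. The downside is a possibly lower reported success rate.
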